10.2.8 Safety Analyses

All safety analyses will be performed on the Safety Analysis Set.

10.2.9 Missing Data

Data from patients who withdraw from the study, including AEs and any follow-up, will be included in the analyses of primary and secondary outcomes.

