- 13. History or evidence of severe peripheral arterial disease in the extremity selected for implant (i.e. arterial inflow insufficient to support hemodialysis)
- 14. History of cancer with active disease or treatment within the previous year, except for non-invasive basal or squamous cell carcinoma of the skin
- 15. Bleeding diathesis, other than that associated with ESRD
- 16. Scheduled renal transplant within 6 months
- 17. Patients who require chronic anticoagulation except for antiplatelet therapy. Patients currently receiving or who have received within the last month direct thrombin inhibitors, factor Xa inhibitors, or vitamin K antagonists should not be included in the study.

Artegraft, Inc.
Protocol: ARTCT.BEACH.001

Data Populations

All patients who receive an Artegraft implant will be included in the safety and performance analyses for the device.

The early-access group is composed of the 50 patients that are enrolled, implanted with the Artegraft, successfully provided the first cannulation within 72 hours, and are followed to 6 months. This early-access population will be used to assess Primary, Assisted Primary, and Secondary Patency at 4, 12, and 26 weeks. This early-access population also will be used to assess perioperative major adverse clinical events (MACE) rates, and all adverse events to 26 weeks.

The late-access group is composed of 25 patients that are enrolled, implanted with the Artegraft, that are first accessed at >/= 10 days, and that are followed to 30 days post Day 0. This group will be used to assess perioperative major adverse clinical events (MACE) rates and primary, assisted primary, and secondary patency, at 30 days post Day 0. The late access group will also be assessed for patency at 6 months through a telephone interview or office visit to provide a more robust data set.

Table 1a: Schedule of Assessments (SoA) Early Access Patients

| Procedure | Screening Day -45 to Day of Surgery | Day 0 [1st successful cannulation] (May occur on day of surgery) | Day 1 – 17 Days post Day 0 | Day 30 +/- 3 days post Day 0 | 12 weeks +/- 7 days post day 0 | 6 Months +/- 7 days post day 0 | 12 Months +/- 14 days post day 0* Extended Follow-up |
|--|--|---|--|--|---|---|--|
| Eligibility (inclusion/exclusion) | Х | | | | | | |
| Informed Consent | Х | | | | | | |
| Medical History | Х | | | | | | |
| Prior and concomitant medication | Х | | Х | Х | Х | Х | |
| Physical Exam | Х | | Х | Х | Х | Х | |

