9.0 STATISTICAL PLAN

9.1 Sample Size Determination

The sample size for this study is logistically rather than statistically driven.

A total of 50 patients will be enrolled, randomized and successfully provided early cannulation within 72 hours, and followed to 6 months. Another group of 25 patients will be randomly assigned and provided cannulation for 10 or more days after implant and followed only to 30 days to assess perioperative MACE rates. No loss to follow-up is projected at 30-days post implantation.

Previously published patency data (refer to the background section above) will be used at 12 weeks and 6 months for clinical context. The early access study group results will be compared with these previously published data, which were reported for Artegraft normal cannulation times. It should be noted that complications may or may not result in an early access failure. Confidence intervals will be presented around each endpoint. The observed rates will be numerically compared with the expected rates and no formal statistical hypothesis will be tested.

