9.2.2 Estimating primary effectiveness and primary safety endpoints

The percentage of patients with primary effectiveness success rates as defined in section 4 will be reported by randomized groups. The 95% confidence interval (CI) calculated using the Clopper-Pearson² exact method for binomial data will be reported by randomized groups. No formal statistical testing of the differences in primary effectiveness rates by randomized groups will be performed.

Similarly, the percentage of patients with MACE together with its 95% CI calculated using the Clopper-Pearson exact method will be reported by randomized groups. The number and percentage of patients in each of the MACE components will also be reported by randomized groups.

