9.2.7 Safety

The safety analysis population will include a subset of patients in the screened analysis population who are implanted with the Artegraft, regardless of whether randomized early or late vascular access is performed. The safety analysis population will be used in reporting safety and product use characteristics.

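### No rule settles how an event-free patient who leaves before Day 30 enters the MACE percentage: one reading understates the rate, the other drops the patient

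*Combined protocol and SAP*

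**What the plan says.** The MACE endpoint runs for 30 days from first cannulation (Day 0) in both groups (Section 4.0). Section 9.2.2 will report, by randomized group, "the percentage of patients with MACE together with its 95% CI calculated using the Clopper-Pearson exact method". Section 10.2.8 adds: "All safety analyses will be performed on the Safety Analysis Set". Section 9.2.7 defines that set as patients "who are implanted with the Artegraft, regardless of whether randomized early or late vascular access is performed", with no minimum follow-up. Section 10.2.9 is the whole of the missing-data plan: withdrawn patients' data, with their adverse events and whatever follow-up exists, "will be included in the analyses of primary and secondary outcomes".

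Section 1.0 (Data Populations) opens by putting all implanted patients into the safety analyses. It then defines the early-access group as 50 patients who are "successfully provided the first cannulation within 72 hours, and are followed to 6 months" and assigns MACE rates to that group. The late-access group, also used for MACE, is made up of patients followed to 30 days after Day 0.

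On expected losses, Section 9.1 says: "No loss to follow-up is projected at 30-days post implantation". Kaplan-Meier is specified in Section 9.2.3 for patency and time to catheter removal, but not for MACE.

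**The concern.** A percentage with a fixed denominator needs every patient's 30-day status. The plan does not say what to do when that status is unknown. Under the safety-set sections, someone followed for 5 days without an event carries the same weight as someone followed for 30. On that reading the error has one sign: it can only lower the reported risk.

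The rate is the primary safety result. It is compared numerically with the roughly 20% expectation in Section 4.0 and is meant to support a labeling change. A denominator chosen after the data are seen could move the figure from one side of 20% to the other.

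**Working it through.** The plan has no figure to reproduce: the sample size is logistic and no hypothesis is tested (Section 9.1).

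**1. Does the zero-loss projection cover the MACE window?** The projection is for 30 days after implantation; the window is 30 days after Day 0.
- Early arm: first cannulation by day 3, so the window closes by about 3 + 30 = day 33. The projection covers nearly all of it.
- Late arm: first cannulation at day 10 or later, so the window closes at day 10 + 30 = 40 or later. The projection leaves at least the last 10 days uncovered.

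**2. Average understatement if event-free leavers count as non-events.**

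Inputs: true 30-day risk p = 0.20 (the Section 4.0 expectation). Assumed: constant hazard, uninformative withdrawal, and fraction withdrawing d.

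- Expected crude rate = (1 − d)·p + d·m, where m is the chance of an event before leaving.
- Hazard h = −ln(0.8)/30 = 0.00744 per day.
- For leaving times uniform on 0 to T, m = 1 − (1 − e^(−hT))/(hT).
- T = 30: m = 1 − 0.2/0.2231 = 0.104.
- T = 7: m = 1 − 0.05074/0.05207 = 0.026.

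| Assumed withdrawals | Leaving uniformly over 30 days | Leaving within 7 days | Understatement (points) |
|---|---|---|---|
| none | 20.0% | 20.0% | 0 |
| 3 of 50 (d = 0.06) | 0.188 + 0.0062 = 19.4% | 0.188 + 0.0015 = 19.0% | 0.6 to 1.0 |
| 5 of 50 (d = 0.10) | 0.180 + 0.0104 = 19.0% | 0.180 + 0.0026 = 18.3% | 1.0 to 1.7 |
| 4 of 25 (d = 0.16) | 0.168 + 0.0166 = 18.5% | 0.168 + 0.0041 = 17.2% | 1.5 to 2.8 |

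A simulation of 8,000 trials per setting agreed to about 0.1 point (its value for 5 of 50 leaving by day 7 was 18.2%, a shift of 1.8). Kaplan-Meier averaged 19.8% to 20.0% throughout.

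**3. One data set, three treatments.** Suppose the early arm has 10 observed events and 3 event-free leavers among 50. Intervals are Clopper-Pearson 95%.

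| Leavers treated as | Rate | 95% CI |
|---|---|---|
| non-events (safety-set reading) | 10/50 = 20.0% | 10.0% to 33.7% |
| excluded (Section 1.0 reading) | 10/47 = 21.3% | 10.7% to 35.7% |
| events (worst case) | 13/50 = 26.0% | 14.6% to 40.3% |

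A single exclusion is enough to pass 20%: 10/49 = 20.4%.

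**4. Patients outside both rules.** The safety set includes implanted patients who are never cannulated. They have no Day 0, so their MACE window is undefined. In the other direction, the six-month condition in Section 1.0, read literally, would also drop early patients who completed the 30-day window but left before six months.

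**The case against.** A reader might infer that the plan, followed as written, biases MACE downward in both arms and always to the sponsor's advantage. The documents do not support that. Section 10.2.9 does not classify an event-free leaver as a non-event; that follows only from combining it with Sections 9.2.2, 9.2.7 and 10.2.8. Section 1.0 points the other way, since excluding the same patients raises the rate. And the bias is exactly zero if nobody leaves before Day 30.

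Losses may indeed be few. Graft sites are assessed at each dialysis treatment (10.2.1), events can be obtained from dialysis centers (10.2), hospital records and survey calls are used (5.1), and a termination visit is requested (6.4). This bears on how many patients are affected, not on how they are counted: a termination visit cannot show events that come after it. Sections 6.4, 9.3 and 9.4 themselves provide for withdrawal and loss, so a projection of none does not replace a rule.

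It is also tempting to say that 26.0% would breach the 20% limit in Section 10.2.6. That figure is a sensitivity bound that treats every unknown as an event. The stopping rule does not use it and is not tied to the final percentage in Section 9.2.2.

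Two further points stand. The average shift is small beside an interval 23.7 points wide (33.7 − 10.0), and no formal conclusion depends on it. Kaplan-Meier assumes uninformative censoring, so it cannot be the only answer.

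**Conclusion.** The point holds as a gap and a conflict, not as an established bias. The plan has no rule for incomplete 30-day follow-up in its primary safety endpoint. The safety-set sections lead by default to counting event-free leavers as non-events, which would understate the rate if any patient withdraws in the window. Section 1.0 would drop them, and nothing chooses between the two.

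The average effect in the early arm is about 0.6 to 1.0 points for 3 of 50 withdrawing and 1.0 to 1.7 points for 5 of 50. These figures rest on a true risk of 20%, constant hazard, uninformative withdrawal and assumed counts; the documents give no withdrawal rate other than the projection of none. That projection does not reach the end of the late-arm window. The change is worth making before results are seen: the effect is modest, but the choice of denominator can decide on which side of 20% the headline figure falls.

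**What to change.** In Section 9.2.2:
- State one MACE denominator: safety-set patients with a Day 0, by randomized group. Reconcile Section 1.0 (Data Populations) with Sections 9.2.7 and 10.2.8 to match.
- Beside the Clopper-Pearson percentage, report a 30-day Kaplan-Meier MACE estimate from Day 0, censored at withdrawal, with a 95% CI. Section 9.2.3 already uses the method for patency.
- Add one sensitivity line counting every event-free patient with incomplete 30-day follow-up as an event. This covers the case where withdrawal is informative.
- Report the number of such patients by arm, and list never-cannulated patients separately.

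The cost is plan wording and a few table rows, with no new patients, visits or data. The downside is that the reported MACE rate may be slightly less favourable.

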10.3 Interim Analyses

No interim analyses for safety or efficacy are planned.

10.4 Safety Monitoring

The principal investigator at each site will perform the initial characterization of each serious event. Reports of serious events will be sent to an independent assessor with expertise in vascular access devices who will evaluate serious device related events, MACE, or device malfunctions for level of seriousness and relationship to device or procedure. Reports of serious adverse events also will be reported to each IRB.

Artegraft, Inc. Version 4.0 21June2019
Protocol: ARTCT.BEACH.001 CONFIDENTIAL Page 51 of 81

An independent accessor will be established to enhance the safety of subjects participating in the study. The accessor will adjudicate all possibly and definitely device and procedure-related serious adverse events and will act as an advisor to Artegraft through the CRO. Individual will be represented from the one of the key medical disciplines involved with the care of ESRD patients and management of AV access. Accessor will not be directly involved with the clinical trial and all will possess experience with clinical trial participation or management in the ESRD or AV access space. Accessor's primary responsibilities are to monitor the safety of trial participants, to review safety-related data, to evaluate the frequency and severity and device-relatedness of adverse events, and to consider external data throughout the duration of the trial, and to make recommendations on trial changes.

Artegraft, Inc.
Protocol: ARTCT.BEACH.001

Version 4.0 CONFIDENTIAL

11.0 DATA HANDLING AND RECORD KEEPING

Data will be collected through an electronic data capturing system on the e-CRF, a secure, internet-based CRF and image transfer software. This system will be used to record all patient information collected in the study for secure data tracking and centralised data monitoring ("remote monitoring").

Automated, real time data analyses built into the database enable complete control on study outcomes and safety assessments. Automated alerts (emails) are generated by the system for enrollment of patients, AE notification, and upcoming or late follow up visits. Additional specific alerts and reports may be setup as required by the Sponsor to ensure full control and easier compliance to the protocol.

The principal investigator or designated site staff (e.g. co-investigators, research/study coordinators or study nurses) at the clinical site will perform primary data collection by entering the data into the e-CRF, using a standard internet-browser. Only the principal investigator or other pre-designated clinical investigation site personnel will be authorised to enter data (from source documents) via internet-based e-CRF, using a unique user name and pass code. Clinical investigation site personnel will each be assigned a unique user name and pass code to access the e-CRF. Each user access to the system is tracked, so that all data operations can be monitored and verified.

The Sponsor's designated monitor shall ensure appropriate training is provided before the start of the clinical investigation to all site personnel involved.

The principal investigator can delegate tasks to his/her collaborators; however, the roles and responsibilities and period of involvement for each clinical site personnel must be documented on the site personnel log as well as training received before getting involved with the clinical investigation.

Clinical site personnel not trained and not officially identified by his/her name, signature and personal login for the EDC system cannot access the system nor enter data in the e-CRFs.

The principal investigator or delegated designee, using his/her personal login information shall enter data in the e-CRF. The monitor, using his/her personal login information shall verify all critical data points against the source documents and issue electronic queries for the authorised clinical site personnel to respond.

After the monitor has done the source document verification and obtained satisfactory answers to eventual queries from the site, a full quality control (QC) will be performed on the monitored data throughout the clinical investigation by the designated data management (DM) team and queries issued where needed. This process will be repeated until the end of the clinical investigation to allow for a lock of the database for statistical analysis.

A CRF section shall be considered complete when all data are completed, verified by the monitor, data cleaning completed, all outstanding queries resolved, pages frozen and signed off by the principal investigator. Only then can the database be locked and ready for statistical analyses.

11.1 Confidentiality

Patient confidentiality will be maintained throughout the clinical study to the extent required by law. Every attempt will be made to remove patient identifiers from clinical study documents and eCRFs. For this purpose, a unique patient identification code will be assigned and used to allow identification of all

Artegraft, Inc. Version 4.0 21June2019
Protocol: ARTCT.BEACH.001 CONFIDENTIAL Page 53 of 81

data reported for each patient. This will also ensure that the information can be traced back to the source data.

Study data may be made available to third parties, e.g., in the case of an audit performed by regulatory authorities, provided the data are treated confidentially and that the subject's privacy is guaranteed, to the extent permitted by law. The identity of a patient will never be disclosed if study data are published.

The Sponsor requires that the study sites comply with the patient confidentiality provisions of the Health Insurance Portability and Accountability Act (HIPAA) issued by the U.S. Department of Health and Human Services (HHS). Sites should maintain patient privacy in accordance to federal regulations (45 CFR Parts 160 and 164), local regulations, and institutional requirements.

11.2 Source Documents

IDE regulations (21 CFR 812) and GCPs require that the Investigator maintain information in the subject's medical records that corroborates data collected on the eCRFs. Throughout the clinical trial duration, the sites' investigators will maintain complete and accurate documentation including but not limited to medical records, clinical trial progress records, laboratory reports, electronic case report forms, signed informed consent forms, device accountability records, correspondence with the IRB and clinical trial monitor or sponsor, adverse event reports, and information regarding patient discontinuation or completion of the clinical trial/investigation. Any source documentation (procedure reports, imaging studies, lab reports, death certificates, etc.) that is sent to the sponsor or reviewing committees should have all patient identifiers removed and replaced with the patient number. To comply with these regulatory requirements/GCP the following information should be included in the patient record at a minimum and if applicable to the investigation:

- Medical history/physical condition of the patient before involvement in the trial sufficient to verify Clinical Investigational Plan entry criteria
- Dated and signed notes on the day of entry into the trial referencing the sponsor, Clinical Investigational Plan number, patient ID number and a statement that informed consent was obtained
- Dated and signed notes from each patient visit (for specific results of procedures and exams)
- Adverse events reported and their resolution including supporting documents such as discharge summaries, ECGs, and lab results including documentation of site awareness of SAEs and of investigator device relationship assessment of SAEs
- Study required laboratory reports and 12-lead ECGs, signed and dated for review and annotated for clinical significance of out of range results
- Notes regarding Clinical Investigational Plan-required and prescription medications taken during the trial (including start and stop dates)
- Subject's condition upon completion of or withdrawal from the trial
- Any other data required to substantiate data entered into the CRF

11.3 Case Report Forms

Primary data collection based on source-documents or clinic chart reviews will be performed clearly and accurately by site personnel trained on the Clinical Investigational Plan and eCRF completion. eCRF data will be collected for all enrolled patients.

11.4 Record Retention

The sponsor will archive and retain all documents pertaining to the trial per the applicable regulatory record retention requirements. The Investigator must obtain permission from Sponsor in writing before destroying or transferring control of any clinical trial/investigation records.

All documentation pertaining to the study will be kept by Artegraft or their designee in accordance with ICH guidelines and US FDA regulations.

The investigator will maintain a study file, which should be used to file the IFU, protocol, and device accountability records; correspondence with the IRB and Artegraft; and other study-related documents. The investigator agrees to keep records and those documents that include (but are not limited to) the identification of all participating subjects, medical records, study-specific source documents, source worksheets, all original signed and dated informed consent forms, query responses, and detailed records of drug disposition to enable evaluations or audits from regulatory authorities and Artegraft or its designees.

The investigator shall retain records required to be maintained under this part for a period of 5 years following the date a marketing application is approved for the drug for the indication for which it is being investigated; or, if no application is to be filed or if the application is not approved for such indication, until 5 years after the investigation is discontinued. However, these documents should be retained for a longer period if required by the applicable regulatory requirement(s) or if needed by the sponsor.

In addition, the investigator must make provision for the subject's medical records to be kept for the same period. No data should be destroyed without the agreement of Artegraft. Artegraft will inform the investigator in writing when the trial-related records are no longer needed. Subject's medical records and other original data will be archived in accordance with the archiving regulations or facilities of the study site.

12.0 STUDY MONITORING, AUDITING, AND INSPECTING

IQVIA BioTech will be managing the trial and will provide statistical management. IQVIA BioTech has assisted Artegraft in preparation of the full Trial Protocol. Trial oversight will be by Artegraft, Inc. via periodic audit.

12.1 Study Monitoring Plan

It is the responsibility of the investigator to ensure that the study is conducted in accordance with the protocol, GCP, applicable regulatory requirements, and the currently approved Declaration of Helsinki, and that valid data are entered in the CRF.

To achieve this objective, the monitor's duties are to aid the investigator and, at the same time, the sponsor, in the maintenance of complete, legible, well-organized, and easily retrievable data. The monitor will review the protocol with the investigator. In addition, the monitor will explain the investigator's reporting responsibilities and all applicable regulations concerning the clinical evaluation of the IP.

The investigator will permit representatives of Artegraft and the CRO to monitor the study as frequently as Artegraft or the CRO deem necessary to determine that data recording and protocol adherence are satisfactory. The CRF data and related source documents will be reviewed in detail by the monitor at each visit, in accordance with relevant SOPs and ICH GCP regulations. This includes results of tests performed as a requirement for participation in this study and any other medical records required to confirm information contained in the CRF such as past medical history and secondary diagnoses. The investigator and his/her staff will be expected to cooperate with the monitor and provide any missing information whenever possible.

All monitoring activities will be reported and archived. In addition, monitoring visits will be documented at the investigational site by signature and date on the study-specific monitoring log.

